## 8.2 Serious Adverse Events

An adverse event or adverse reaction is considered serious if, in the view of either the Investigator or Sponsor, it results in any of the following outcomes:

- Death.
- A life-threatening adverse event.

Note: An adverse event or adverse reaction is considered “life-threatening” if, in view of either the Investigator or Sponsor, its occurrence places the patient at immediate risk of death. It does not include an event that, had it occurred in a more severe form, might have caused death.

- Requires hospitalization or prolongation of existing hospitalizations.

Note: Any hospitalization over 24 hours will be considered an inpatient hospitalization. An emergency room or urgent care visit without hospital admission will not be recorded as an SAE under this criterion, nor will hospitalization for a procedure scheduled or planned before signing of informed consent, or elective treatment of a pre-existing condition that did not worsen from Baseline. However, unexpected complications and/or prolongation of hospitalization that occur during elective surgery should be recorded as adverse events and assessed for seriousness. Admission to the hospital for social or situational reasons (i.e., no place to stay, live too far away to come for hospital visits, or respite care) will not be considered inpatient hospitalizations.

- A persistent or significant disability/incapacity or substantial disruption of the ability to conduct normal life functions.
- A congenital anomaly/birth defect.
- An important medical event.

Note: Important medical events that do not meet any of the above criteria may be considered an SAE when, based upon appropriate medical judgment, they may jeopardize the patient and may require medical or surgical intervention to prevent one of the outcomes listed above. Examples of such medical events include allergic bronchospasm requiring intensive treatment in an emergency room or at home, blood dyscrasias or convulsions that do not result in inpatient hospitalizations, or the development of drug dependency.

### **8.3 Serious Adverse Event Reporting – Procedures for Investigators**

#### Initial Reports

All SAEs occurring from the time of informed consent until the EOS/ET Visit must be entered into the electronic data capture (EDC) system within 24 hours of the knowledge of the occurrence.

To report the SAE, complete the SAE form electronically in the EDC system for the study. When the form is completed, Medpace Safety personnel will be notified electronically by the EDC system and will retrieve the form. Flexion Pharmacovigilance will also receive notification. If the event meets serious criteria and it is not possible to access the EDC system, send an email to Medpace Safety at [[contact]](mailto:[contact]) or call the Medpace SAE Reporting Line (phone number listed below), and fax/email the completed paper SAE form to Medpace (fax number listed below) within 24 hours of awareness. When the EDC system becomes available, the SAE information must be entered within 24 hours of the system becoming available.

Safety Contact Information: Medpace Clinical Safety

Medpace SAE reporting line – USA:

[contact], dial 3 or [contact], dial 3

[contact] or [contact]

E-mail: [[contact]](mailto:[contact])

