### 4.3 Withdrawal Criteria

If a patient withdraws, he/she should continue to be followed for safety assessments up to 24 weeks after treatment. A patient may withdraw from the study at any time for any reason, without any consequences. In addition, a patient may be withdrawn from the study for the following reasons:

- Adverse event (typically a serious adverse event [SAE])
- Patient choice (withdrawal of consent, Investigator will attempt to ascertain reason)
- Protocol violation/noncompliance
- Lack of efficacy (lack of expected or desired effect related to a therapy)
- Physician decision (a position, opinion, or judgment reached after consideration by a physician with reference to the patient)
- Progressive disease (a disease process that is increasing in extent or severity)
- Study terminated by Sponsor
- Technical problem (a problem with some technical aspect of a clinical study, usually related to an injection)
- Other

If a patient withdraws from the study, he/she may request destruction of any samples taken and not tested, and the Investigator must document this in the study site records.

If a patient withdraws prematurely from the study due to the above criteria or any other reason, study staff should make every effort to complete the full panel of assessments scheduled for the EOS Visit (Week 24) (see Section 6.6). The reason for patient withdrawal must be documented in the electronic case report form (eCRF). Those patients who withdraw from the study will be referred to a physician for follow-up care.

Withdrawn patients will not be replaced.

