#### 6.6 Early Termination Visit and Withdrawal Procedures

The end of treatment for patients completing the study is the EOS Visit (Week 24). For patients who withdraw from the study prior to completion (Early Termination [ET]), all EOS Visit procedures will be performed at the corresponding visit. See Section 6.5.2 for the procedures that will be performed.

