## **8 SAFETY ASSESSMENTS**

### **8.1 Adverse Events**

Patients will be monitored for adverse events from the time of informed consent through the end of their participation in the study.

An adverse event is defined as any untoward medical occurrence in a clinical investigation patient administered a pharmaceutical product, which does not necessarily have a causal relationship with this treatment. An adverse event can therefore be any unfavorable and/or unintended sign (including an abnormal laboratory finding), symptom, or disease temporally associated with the use of an investigational medicinal product, whether or not related to the investigational medicinal product.

Patients should be instructed to report any adverse event that they experience to the Investigator, whether or not they think the event is due to study medication. Beginning at the time of informed consent, Investigators should make an assessment for adverse events at each visit and record the event on the appropriate adverse event eCRF.

Wherever possible, a specific disease or syndrome rather than individual associated signs and symptoms should be identified by the Investigator and recorded on the eCRF. However, if an observed or reported sign or symptom is not considered a component of a specific disease or syndrome by the Investigator, it should be recorded as a separate adverse event on the eCRF. For example, a diagnosis of ‘influenza’ should be reported as an adverse event instead of the symptoms of fever, fatigue, malaise, and positive flu test. Additionally, the condition that led to a medical or surgical procedure (e.g., surgery, endoscopy, tooth extraction, or transfusion) should be recorded as an adverse event, not the procedure itself.

Any medical condition already present at the time of informed consent should be recorded as medical history and not be reported as an adverse event unless the medical condition or signs or symptoms present at Baseline changes in severity, frequency, or seriousness at any time during the study. In this case, it should be reported as an adverse event.

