
 
1. For patients who are withdrawn from the study prior to completion, all EOS Visit procedures will be performed at the corresponding visit.
 
2. Written informed consent must be obtained prior to performing any study-specific procedures.
 
3. Must be collected or assessed prior to administration of study medication.
 
4. To be completed prior to questionnaires completed at study site visits.
 
5. To be completed after APR and PRR training, but prior to any other assessments.
 
6. These assessments will be collected daily each evening in the eDiary and reviewed (not completed) at site visits.
 
7. To include assessment of active and passive ranges of motion per standardized measurement protocol. Performed bilaterally (index and contralateral) at the Screening Visit.
 
8. X-ray of shoulder will include axillary view and true anterior-posterior view to be taken at the Screening Visit (or within 6 weeks of the Screening Visit) and read centrally to confirm eligibility criteria are met.
 
9. To be analyzed by the Central Laboratory.
 
10. Pregnancy tests will be performed in women of childbearing potential only. Follicle-stimulating hormone in perimenopausal women who have not had a menstrual period for 1 year will be measured at the Screening Visit.
 
11. After signing the ICF, patients must stop taking excluded medications (see Section 5.6.1). Excluded medication washout should be for 5 half-lives of the medication and be completed 7 days prior to Day 1.
 
12. Aspiration must be attempted prior to the injection. If effusion is detected by ultrasound guidance, injector must withdraw to near dryness prior to the injection.
 
13. Patients will be registered in the eDiary and provided instructions on its use.
 
14. Rescue medication will be dispensed to patients at the Screening Visit. At each subsequent visit, rescue medication accountability will be performed and additional rescue medication will be returned/dispensed as needed.
 
15. Rescue medication will be returned but not dispensed at the EOS/ET Visit.
 
16. Shoulder AC patients will follow a HEP beginning 3 days postinjection through the EOS/ET Visit and record their compliance daily via eDiary.
 
17. Adverse events will be assessed from the time of informed consent until the end of patient participation in the study.
 
18. Concomitant medication(s) will be captured from the time of informed consent until the end of patient participation in the study.
 
 
AC = adhesive capsulitis; APR = Accurate Pain Reporting; ASES = American Shoulder and Elbow Surgeons Standardized Shoulder Assessment Form; BMI = body mass index; ECG = electrocardiogram; eDiary = electronic diary; EOS = End of Study; EQ-5D-5L = EuroQol 5 Dimensions 5 Levels; ET = Early Termination; FSH = follicle-stimulating hormone; GAD-7 = General Anxiety Disorder 7-item scale; HBsAg = hepatitis B surface antigen; HCV = hepatitis C virus; HEP = Home Exercise Program; HIV = human immunodeficiency virus; ICF = informed consent form; ISI = Insomnia Severity Index; OA = osteoarthritis; PCS = Pain Catastrophizing Scale; PD-Q = painDETECT Questionnaire; PGIC = Patient Global Impression of Change; PHQ-9 = Patient Health Questionnaire-9; PRR = Placebo Response Reduction; SI = Sleep Interference; SPADI = Shoulder Pain and Disability Index.
				

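### The 24-week safety follow-up of withdrawn patients in Section 4.3 is not carried through to the SAE entry window in Section 8.3 or to the schedule in Table 1

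*Combined protocol and SAP*

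**What the plan says.** Section 4.3 (Withdrawal Criteria) sets the follow-up: "If a patient withdraws, he/she should continue to be followed for safety assessments up to 24 weeks after treatment". The same section also says: "Those patients who withdraw from the study will be referred to a physician for follow-up care".

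Section 8.3 (Initial Reports) sets the entry duty: "All SAEs occurring from the time of informed consent until the EOS/ET Visit must be entered into the electronic data capture (EDC) system". The deadline for entry is 24 hours from knowledge of the event.

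Section 6.6 describes what happens at early termination: "all EOS Visit procedures will be performed at the corresponding visit". Footnote 1 of Table 1 (Appendix A) repeats this: "For patients who are withdrawn from the study prior to completion, all EOS Visit procedures will be performed at the corresponding visit". The last column of Table 1 is Week 24, labelled EOS/ET (End of Study or Early Termination). No visit or call follows it.

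AEs in general have a differently worded end point. Section 8.1: "Patients will be monitored for adverse events from the time of informed consent through the end of their participation in the study". Table 1, footnote 17: "Adverse events will be assessed from the time of informed consent until the end of patient participation in the study". Section 10.3 defines study completion for a patient and the end of the study as a whole. It does not say when participation ends for someone who has withdrawn.

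**The concern.** For a patient who completes Week 24, the follow-up period and the SAE entry window end together. For a patient who withdraws early they separate at the ET Visit. From then on Section 4.3 still asks for safety follow-up, but no section gives it a schedule, a method or an entry requirement.

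Two things are at stake:

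- **Reporting.** The 7-day and 15-day expedited reporting limits in Section 8.6 run from the time the sponsor or its designee learns of the event. A site that works from Section 8.3 and Table 1 as written has no explicit task that would bring a new post-ET SAE to light.
- **Analysis.** The Safety Population (Section 9.3) keeps every dosed patient. Section 9.4.2.1 counts events that start or worsen after dosing, states no end date, and reports SAEs in the same number-and-percent form. A post-ET event would meet that definition, but collection may already have stopped while the patient stays in the denominator. If early withdrawal differs between arms, so does the time over which events could be seen. Adverse events and lack of efficacy are among the listed withdrawal reasons, so a difference is possible.

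**Working it through.** The plan gives no figure to reproduce here. The check is a comparison of sections plus one subtraction.

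**Step 1: end points for a patient who withdraws early but still allows contact**

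| Source | Subject | Ends at |
|---|---|---|
| Section 4.3 | Safety follow-up (worded as *should*) | As late as 24 weeks after injection |
| Section 8.3, Initial Reports | EDC entry of SAEs (worded as *must*) | ET Visit |
| Section 6.6; Table 1, footnote 1 | Scheduled procedures | ET Visit |
| Section 8.1; Table 1, footnote 17 | AE monitoring | End of participation, undefined for this patient |

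**Step 2: does any other section close the gap?**

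- Section 8.3, Follow-Up Reports: SAEs are followed until they resolve or consent is withdrawn. This covers an SAE that began before ET. It does not extend the window for a new one.
- Section 8.4: index-shoulder changes are reportable with no stated ET cut-off, but serious ones are sent back to Section 8.3 and so meet the same limit.
- Section 8.6: sponsor reporting has no ET limit, but depends on the sponsor learning of the event.
- Section 11.9: the investigator notifies the IRB of SAEs as IRB procedures require. This is not a route for active collection or EDC entry.
- Section 8.1: investigators assess AEs at each visit, and none is scheduled after ET.
- Section 4.3: referral to a physician for follow-up care creates no reporting route to the sponsor.

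None of these supplies a post-ET contact or a duty to enter a new SAE.

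**Step 3: largest uncovered time per patient**

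Inputs: 24 weeks (Section 4.3) and the nominal post-dose visits before Week 24, which are Weeks 1, 4, 8, 12, 16 and 20 (Section 3.1). Visit windows of ±3 days are ignored.

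Uncovered weeks = 24 − ET week

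| ET at Week | Calculation | Weeks uncovered, at most |
|---|---|---|
| 1 | 24 − 1 | 23 |
| 4 | 24 − 4 | 20 |
| 8 | 24 − 8 | 16 |
| 12 | 24 − 12 | 12 |
| 16 | 24 − 16 | 8 |
| 20 | 24 − 20 | 4 |
| 24 | 24 − 24 | 0 |

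The documents give neither a withdrawal rate nor a rate of late SAEs, so neither total lost follow-up nor an expected number of missed events can be computed.

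**The case against.** The strongest reply is that nothing here strictly contradicts anything else. Section 4.3 says *should* and sets an upper limit on follow-up. Section 8.3 says *must* and concerns data entry. A site can satisfy both, and Section 8.3 does not forbid entering a later event. This stands: the fault is that Section 4.3 is not carried through, not that two rules collide. The fault remains, because a site following the Section 8.3 cut-off exactly has no explicit entry duty during follow-up that the protocol itself asks for.

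A second reply is that a patient still in safety follow-up is still participating, so Section 8.1 and footnote 17 already cover the period. That reading is reasonable. So is the opposite one, since the term is undefined for a withdrawn patient. The ambiguity narrows the clearest mismatch to the Section 8.3 sentence, which names the ET Visit outright.

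A reader might try to settle the ambiguity the other way, by setting footnote 18 of Table 1 ("Concomitant medication(s) will be captured from the time of informed consent until the end of patient participation in the study") beside Section 5.6, which ends concomitant therapy at the EOS Visit, and inferring that participation stops at ET. The documents do not support this. Section 6.5.2 identifies the EOS Visit as Week 24, and Section 6.6 names Early Termination separately. If anything, the pairing points towards Week 24. Section 5.6 also defines medications, not AE collection.

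It is also fair to say that patients who withdraw consent to follow-up cannot be followed under any wording.

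**Conclusion.** The point holds as a failure to carry Section 4.3 through to Sections 6.6 and 8.3 and Table 1. It applies only to patients who withdraw early and still allow contact. For them, a new SAE after ET has no explicit duty of active collection or EDC entry and could go unreported to the sponsor. SAEs that began before ET are still followed, and patients who complete Week 24 are unaffected.

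The size is at most 23 weeks per patient for ET at Week 1, falling to 4 weeks for ET at Week 20. This rests on nominal visit weeks and on reading the Section 4.3 follow-up at its full 24 weeks.

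Two stronger readings go beyond the documents. A reader might take the weeks as a measure of missed events, but without withdrawal or late-SAE rates they show only time. A reader might also conclude that post-ET SAEs, including those needing expedited reporting, will be lost. The text shows only that nothing explicitly requires sites to seek or enter them. An event may still reach the sponsor, and Section 8.6 would then apply.

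**What to change.** Reconcile Sections 4.3, 6.6, 8.1 and 8.3 and Table 1 with its footnotes:

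1. Define the end of participation for a patient who has withdrawn.
2. For injected patients who have not withdrawn consent to follow-up, make the AE and SAE collection and entry window match the safety follow-up in Section 4.3.
3. List the post-ET safety contacts in Table 1, for example by telephone.

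If follow-up after ET is not intended, correct Section 4.3 instead, so that all sections end at the same point.

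The cost is amendment wording and a few calls per withdrawn patient, with no new staff or procedure. Some patients will decline, so follow-up will remain incomplete for them.

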#### Follow-Up Reports

The Investigator is required to follow SAEs until resolution or withdrawal of consent. Resolution is defined as:

- A return to Baseline for a pre-existing condition.
- Resolved with or without residual effects.
- The Investigator does not expect any further improvement or worsening of the event.

Within 24 hours of receipt of follow-up information, the Investigator must update the SAE form electronically in the EDC system for the study and submit any requested documentation (e.g., patient discharge summary or autopsy reports) to the Sponsor via e-mail. If it is not possible to access the EDC system, refer to the procedures outlined above for initial reporting of SAEs.

#### Fatal Outcomes

If an autopsy is performed on a deceased patient, the autopsy report should be provided to the Medical Monitor and Flexion Pharmacovigilance as soon as it is available.

### **8.4 Clinical Management of Index Shoulder-Related Events**

In the event the patient has an immediate reaction following administration of study medication or returns to the clinic with an acute exacerbation (e.g., tenderness, increased pain, swelling, effusion, or decreased mobility of the index shoulder), the patient should be treated according to local clinical guidelines and physician experience.

If the index shoulder is aspirated at any time other than administration of study medication for any reason, the volume of synovial fluid aspirated must be documented, synovial fluid should be (1) cultured, (2) evaluated for the presence of crystals, and (3) assessed for white cell count at a local laboratory, and the results should be documented.

Any event that is a change from the patient's Baseline status (new or worsening case) should be reported as an adverse event and those meeting the definition of an SAE must be reported in accordance with Section 8.3.

### **8.5 Pregnancy Reporting**

A pregnancy is not considered to be an adverse event or SAE; however, it must be reported to Medpace Clinical Safety within 24 hours of knowledge of the event. Medpace Clinical Safety will then provide the Investigator/site the Exposure In Utero (EIU) form for completion. The Investigator/site must complete the EIU form and fax or e-mail it back to Medpace Clinical Safety.

If the female partner of a male patient becomes pregnant during the study, the Investigator should notify Medpace Clinical Safety as described above.

The pregnancy should be followed until the outcome of the pregnancy, whenever possible. Once the outcome of the pregnancy is known, the Exposure In Utero form should be completed and emailed to Medpace Clinical Safety. If the outcome of the pregnancy meets the criteria for immediate classification as an SAE (i.e., postpartum complication, spontaneous abortion, stillbirth, neonatal death, or congenital anomaly), the Investigator should follow the procedures for reporting an SAE. Additional subsequent follow-up is not needed when a newborn baby is healthy.

### **8.6 Expedited Reporting**

The Sponsor/designee will report all relevant information about Suspected Unexpected Serious Adverse Reactions (SUSAR) that are fatal or life-threatening as soon as possible to the Food and Drug Administration (FDA), and in any case no later than 7 days after knowledge by the Sponsor/designee of such a case. Relevant follow-up information will subsequently be communicated according to the required regulatory timelines.

All other SUSAR will be reported to the FDA as soon as possible but within a maximum of 15 days of first knowledge by the Sponsor/designee.

The Sponsor/designee will also report any additional expedited safety reports required in accordance with the timelines outlined by the FDA.

The Sponsor/designee will also inform all Investigators as required per local regulation.

The requirements above refer to the requirements relating to an investigational medicinal product.

### **8.7 Reporting Arthralgia in the Index Shoulder**

Since all enrolled patients are required to have a certain level of arthralgia in the index shoulder before they receive study medication, the Investigator must take care to fully assess any patient reports of index shoulder arthralgia that occur during the study. Incremental return of pre-existing index shoulder arthralgia following postinjection pain relief does not meet the criteria for an adverse event unless the arthralgia is clinically significantly worse from Baseline (before study medication administration).

Changes in the patient's typical average daily shoulder pain with movement, which serves as the primary efficacy outcome measure, will be assessed utilizing the NRS scale via the daily eDiary and would not meet the criteria for an adverse event of arthralgia unless the pain has clearly worsened relative to Baseline. However, any new arthralgia, including any new type of arthralgia in the index shoulder joint, should be recorded as an adverse event.

